## **6.0 Research Data Protection and Reporting**

### **6.1 Data Management and Confidentiality**

- A. Primary outcome measures of daily median pain scores will be compared using nonparametric statistical methods. Survey responses will also be compared using Chi-square for proportions, and non-parametric methods for ordinal data.
- B. Power analysis is not performed as this is a pilot study.
- C. No PHI will be recorded in any datasheet. Data sheets will be maintained in a password protected file on the password protected principle investigators' laptop.
- D. Because all data will be collected at the time of subject discharge, data should be complete and clean for each individual at the time of collection.

Version Number: 5

Protocol Number: Pro2018001008

PI Name: [name]

Protocol Title: TENS after Cesarean Delivery

13

RESERVED FOR IRB STAMP

DO NOT MODIFY THIS SPACE

IRB ID: Pro2018001008

Approval Date: 7/19/2022

Expiration Date: 7/18/2023

**E.** Data will be shared through University secure email among study investigators only. Source data will be destroyed following data analysis, anticipated to be 1 year after completion of study procedures.

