## **6.3 Data and Safety Monitoring**

### **A. Periodic Data Evaluation**

Data will be evaluated after pairs of intervention and control subjects are enrolled to compare differences. If 3 consecutive sets of intervention/controls demonstrate worse outcomes for intervention subjects, the study will be suspended. Additionally, interim data analysis will be performed by the project statistician after enrollment of 50% of subjects to ensure that device usage does not cause increased pain.

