TENS and Opioid Use After Cesarean Delivery

NCT03843788

Document Type: Statistical Analysis Plan

Document Date: 7/11/2024

Statistical Analysis Plan

All outcomes will be presented using descriptive statistics; normally distributed data by the mean and standard deviation (SD) and skewed distributions by the median and interquartile range (IQR).

Primary Outcome

The primary analysis will compare intervention groups (TENS vs usual care) on mean change in pain score as measured by Visual Analog Scale (VAS) over the course of the inpatient hospital stay. Measured primary outcomes were pain ratings, number and type of pain medications used, and patient satisfaction with pain control. Fixed effects repeated measures analysis of variance was used to evaluate the differences in pain scores between groups and Mann-Whitney tests were used to examine differences in medication intake. Additionally, repeated measures correlation (RMCORR) between TENS and usual care arms with an exploratory analysis of pain behavior in individuals with SUD compared to no SUD will be performed.

Secondary outcomes

Secondary outcomes will include pain surveys at 6 weeks postoperatively, time to first bowel movement, level of sedation, and time to out-of-bed (OOB).

Missing data

Mixed-effects procedure was utilized to avoid loss of data from missing values at different time points.

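### The SAP's departures from the protocol's primary analysis are not shown to predate data by arm, so they should be labelled post hoc unless an earlier dated plan is produced

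*SAP*

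**What the plan says.** Protocol section 6.1, item A, gives the only analysis that the protocol calls primary: "Primary outcome measures of daily median pain scores will be compared using nonparametric statistical methods". The same item assigns chi-square or nonparametric methods to survey responses. It gives no test for medication use.

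The SAP carries the line "Document Date: 7/11/2024". Its text mixes tenses. In the past tense:

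- outcomes: "Measured primary outcomes were pain ratings, number and type of pain medications used, and patient satisfaction with pain control"
- tests: "Fixed effects repeated measures analysis of variance was used to evaluate the differences in pain scores between groups and Mann-Whitney tests were used"
- missing data: "Mixed-effects procedure was utilized to avoid loss of data from missing values at different time points"

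In the future tense are the statement that the primary comparison is on mean change in VAS pain score, the repeated measures correlation (RMCORR), the secondary outcomes, and the "exploratory analysis of pain behavior in individuals with SUD compared to no SUD will be performed".

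On access to results, protocol section 6.3.A says: "Data will be evaluated after pairs of intervention and control subjects are enrolled to compare differences". It adds an interim analysis by the project statistician at half enrolment. Sections 6.3.B, D and E say that the data reviewed are median daily pain score and survey results, that they are collected after each pair, and that the statistician is one of three reviewers.

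**The concern.** A document titled as a statistical analysis plan will be read as having been fixed before the results were known. Here the date is late, the main tests are described as already carried out, and the protocol planned for the statistician to see the primary outcome by arm as pairs accrued. If the outcome form or the model was settled after such a look, the p-value does not have its nominal error rate and the effect estimate may be biased upward by selection. The estimate matters even in a pilot, because section 1.5 says this study is to be the basis for larger trials powered on pain scores.

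This is separate from the mismatch between protocol and SAP. Rewording one document to agree with the other would not show when the choice was made.

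**Working it through.** **1. What is new in the SAP, set against the protocol**

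| Element | Protocol | SAP | Status |
|---|---|---|---|
| Inpatient pain compared between arms | Primary (6.1.A) | Primary | Already planned |
| Form of the pain outcome | Daily median score | Mean change in VAS | Departure |
| Pain method | Nonparametric | Repeated measures ANOVA; a mixed-effects procedure is also named | Departure |
| Medication use and satisfaction | Named as outcomes (1.6.B), not called primary in 6.1.A | Listed as primary | Departure in rank |
| Test for medication use | None given | Mann-Whitney | New choice |
| RMCORR | Absent | Added | Departure |
| Opioid-history comparison | Design category (1.3, 1.5) and stated hypothesis (1.1.B) | Exploratory SUD analysis | Question planned; only the method is new |

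**2. Dates**

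No document gives the date of last visit, data lock, first comparison by arm or first test run. The available dates only bracket the gap.

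- End of the approval period printed on the protocol, 18 July 2023, to 11 July 2024: 366 − 7 = 359 days, or 359 / 30.4375 = 11.8 months.
- If a last subject had enrolled on 18 July 2023 and stayed for the 12-week maximum in section 1.3, follow-up would end on 10 October 2023. The gap to the SAP is 275 days, about 9.0 months. This assumes that approval was not renewed.
- On the protocol's own timetable (July 2018 start in section 4.2.A, up to 9 months of recruitment in section 1.5, 12 weeks per subject), taking 1 July 2018 as the start, follow-up would end about 24 June 2019. The gap is 1,844 days, about 61 months. The protocol copy carries a July 2022 approval, so this timetable may well have slipped.

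**3. Planned looks by arm**

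Section 1.5 gives 5 + 5 + 5 + 5 = 20 subjects, hence 20 / 2 = 10 pairs: up to 10 pairwise looks plus one interim analysis. (Section 4.5.C gives 40 as the number required to complete; that figure needs reconciling separately.) The looks cover the protocol's primary outcome and the surveys. Medication use is not on the list in section 6.3.B.

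**4. Size of the possible effect on error**

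The documents state no alpha, so 0.05 is assumed. Take four candidate tests: a rank test on daily medians, the arm effect in the ANOVA, the arm-by-time effect, and the medication test. The chance of at least one p < 0.05 when there is no effect is:

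- all four independent: 1 − 0.95^4 = 1 − 0.8145 = 0.185
- the three pain tests fully dependent, medication independent: 1 − 0.95^2 = 0.0975
- all four fully dependent: 0.05

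The first three tests use the same pain scores, so independence is unlikely. The four-test list is an illustration and is not taken from the documents.

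**The case against.** The strongest reply has four parts.

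*The protocol already contains much of the SAP.* This stands. The between-arm pain comparison, the outcomes themselves and the opioid-history hypothesis are in the protocol, and less opioid use is its first objective. A reader might infer that nothing in the SAP was prespecified; the documents do not support that. Calling the SUD comparison post hoc would also be wrong, since section 1.1.B states the hypothesis and the SAP already calls the analysis exploratory.

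*The timing evidence is indirect.* This also stands. Several SAP statements are in the future tense, a document date need not be the date on which methods were chosen, and 18 July 2023 is only the end of one approval period. A reader might take the 359 days as proof that the SAP followed the results. It is not proof. There is one further hint: section 6.1, item D, expected complete data, whereas the SAP describes in the past tense a remedy for missing values. That suggests the data had been seen, but it does not settle the matter.

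*The looks were planned, not reported.* This stands too. A reader might infer that the investigators had watched the arms diverge and then chose the tests. Nothing shows that any look took place, two of the three reviewers are not identified in the public text, and medication was not among the data to be reviewed.

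*The protocol's own primary analysis is thin, and this is an unpowered pilot.* Section 6.1 names no particular test and no rule for combining days, and section 1.3 gives the primary endpoint as an enrolment count. That limits how far section 6.1 can serve as a full prespecification. It still fixes the outcome (daily median) and the class of method (nonparametric), and the SAP changes both.

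What none of this supplies is evidence that the changes were made before data by arm were available.

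**Conclusion.** The point holds for the departures only: mean change in VAS, the repeated measures ANOVA or mixed-effects procedure, medication use and satisfaction as primary outcomes, the choice of Mann-Whitney for medication, and RMCORR. On the documents as they stand, these cannot be presented as prespecified. That conclusion rests on the late date, the past-tense description of the main tests, the planned access to results by arm, and the absence of any earlier dated plan. It does not require that the looks took place, and it makes no finding that the results drove the choices.

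The effect on error is uncertain. At an assumed alpha of 0.05 it lies between no inflation (about 5%) and 18.5% for a choice among four tests, and dependence among the pain tests makes the upper end unlikely. This is an illustration of scale, not an estimate of the trial's actual error rate. The practical consequence is which result may be reported as the trial's primary one.

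**What to change.** 1. Report the section 6.1 analysis (daily median pain score, nonparametric comparison of arms) as the prespecified primary result. State the particular test and how days are combined, and say that these details were settled later.
2. In the SAP, the registry entry and any paper, label each departure listed in the verdict post hoc, unless an earlier dated plan containing it is produced.
3. Keep the SUD comparison as exploratory, and note that only its method is new.
4. Report all of these analyses whatever they show.
5. Support the labels with three dates in the SAP: last data collection, first comparison by arm, and first run of these tests. If the pairwise looks did not take place, say so.

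The cost is one extra analysis, a short paragraph and some labels. All of it can be done after data collection. The drawback is that the relabelled results carry less weight.

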#### **A. Objectives**

- To determine if the addition of TENS therapy to the pain management of women post-C-Section leads to less opioid medication use.
- To evaluate the efficacy of TENS therapy as a means of alternative pain relief for women post-C-section (CS) and for postpartum women with a history of opioid use.

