#### **B. Hypotheses / Research Question(s)**

Version Number: 5

Protocol Number: Pro2018001008

PI Name: [name]

Protocol Title: TENS after Cesarean Delivery

3

RESERVED FOR IRB STAMP

DO NOT MODIFY THIS SPACE

IRB ID: Pro2018001008

IRB Form Version 01/2018 Approval Date: 7/19/2022

Expiration Date: 7/18/2023

We hypothesize that patients that receive TENS therapy will report lower pain scores and request less opioid medication than the control group. We anticipate improved control in particular in the group of women with a history of opioid use.

Additionally, we believe that the TENS therapy will show benefits in other postpartum outcomes including time to bowel movement, level of sedation, and time to out of bed.

Overall, we anticipate that this pilot study will support the application of TENS therapy in postpartum pain management.

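### The SAP compares TENS with usual care without using opioid-history category, within which 5 v 5 is planned, and does not clearly plan a TENS effect in each category.

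*SAP*

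**What the plan says.** Protocol 1.3 (Overview; Primary and Secondary Endpoints) and 1.5 divide 20 women into two categories, with and without a history of opioid addiction, and plan 5 TENS and 5 control in each. Section 1.1 A sets the first objective as finding out whether adding TENS "leads to less opioid medication use". Section 1.1 B adds: "We anticipate improved control in particular in the group of women with a history of opioid use". That is a statement about how the TENS effect differs between categories.

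The SAP's primary contrast is TENS v usual care on "mean change in pain score as measured by Visual Analog Scale (VAS"). It then says "Fixed effects repeated measures analysis of variance was used to evaluate the differences in pain scores between groups and Mann-Whitney tests were used" for medication intake. Category appears once, as an "exploratory analysis of pain behavior in individuals with SUD compared to no SUD", in the sentence that also proposes "repeated measures correlation (RMCORR) between TENS and usual care arms". Under Missing data the SAP says "Mixed-effects procedure was utilized to avoid loss of data from missing values at different time points".

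Protocol 6.1 A, which plans nonparametric comparison of daily median pain scores, does not mention category either. Section 6.1 B says that no power analysis was done because this is a pilot.

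**The concern.** A design that fixes the arm split within categories would normally carry the category into the analysis. If it is left out and the categories differ in pain or intake, their difference stays in the error term: the test rejects too rarely and the interval is too wide. One category is defined by methadone or Subutex use (protocol 4.2 D), so a difference in intake is plausible, though the documents give no figure for it.

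The second issue is the hypothesis in 1.1 B, which needs TENS v control within each category, or the difference between those two effects. The SUD clause could mean that. It could equally mean a contrast of the two patient types regardless of arm. It also speaks of pain behaviour and does not mention medication intake, the subject of the first objective. Protocol 1.5 says the pilot is to support larger trials, so estimates and interval widths are its useful products.

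**Working it through.** **Inputs from the documents.** 2 categories x 2 arms x 5 = 20, which reproduces the planned total in protocol 1.5. TENS starts 8 hours after surgery (1.3).

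**Assumptions.** Two-sided 5% level; normal outcomes with SD 1 within category; category gaps of 0 to 2 SD; correlation between starting and later pain of 0.5 or 0.7. The illustrative effect comes from Table 1 in protocol 1.4, POD-1: difference 0.532 - 0.362 = 0.170; pooled SD sqrt[(25 x 0.173² + 23 x 0.280²)/48] = 0.231; ratio 0.737 SD. That trial combined TENS with physiotherapy, and the same section cites another with no significant between-arm difference.

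**Why there is no bias with 5 v 5.** Let the category means be a and a + g. Each arm then has mean a + g/2 before any TENS effect, so g cancels from the difference. It does not cancel from the variance. Within an arm it adds 10(g/2)²/9 = 0.278g², so at g = 1 the estimated SE is about sqrt(1.278) = 1.13 times too large.

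**Pain** (simulation, one starting and one later score, least squares).
- If levels are compared without a starting score, power at gaps of 1/1.5/2 SD is 26/18/10% without category and 34% with it.
- If change is compared, as the SAP's first sentence on the primary outcome says, a stable gap cancels. The average 95% half-width is 0.93 SD at correlation 0.5 and 0.72 SD at 0.7, whatever the gap.
- With the starting score and category as covariates, it is 0.83 and 0.69 SD.

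Half-widths with the starting score, before and after adding category:

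| Gap (SD) | Corr. 0.5: without | with | Corr. 0.7: without | with |
|---|---|---|---|---|
| stable 1 | 0.854 | 0.834 | 0.693 | 0.688 |
| stable 1.5 | 0.873 | 0.834 | 0.699 | 0.688 |
| stable 2 | 0.887 | 0.834 | 0.705 | 0.688 |
| 1 growing to 1.5 | 0.938 | 0.834 | 0.770 | 0.688 |
| 1 growing to 2 | 1.066 | 0.834 | 0.896 | 0.688 |

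Category therefore narrows the interval by 1-6% if the gap is stable and by about 11% or 22% if it grows (for example 1 - 0.834/0.938 = 11%). With no gap it widens it by about 0.5%. Compared with the change analysis, most of the gain at stable gaps of 1 or 1.5 SD comes from the starting score. At 2 SD the two steps are about equal.

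**Medication** (40,000 simulated trials per setting, 5 v 5 enforced, simulation error about 0.2 points). The pooled exact Mann-Whitney test rejects at U <= 23 of 100 or the mirror value (size 4.33%). The stratified exact test sums two 5 v 5 statistics and rejects at U <= 11 of 50 or the mirror value (size 4.41%). In the second case below, TENS lowers intake by 1.474 SD in the opioid-history category, assumed to have the higher intake, and by nothing in the other, so the mean effect is again 0.737 SD.

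| Gap (SD) | Equal effect: pooled | stratified | Opioid-history only: pooled | stratified |
|---|---|---|---|---|
| 0 | 31% | 30% | 21% | 21% |
| 0.5 | 28% | 30% | 25% | 21% |
| 1 | 22% | 30% | 25% | 21% |
| 1.5 | 14% | 30% | 21% | 21% |
| 2 | 8% | 30% | 14% | 21% |

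With no TENS effect, the pooled test's type I error at gaps of 1/1.5/2 SD is 2.5/1.1/0.4%, against 4.4% stratified.

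**By category**, 5 per cell, no starting score: half-width of the TENS effect = sqrt(2/5) x t(16) = 0.632 x 2.12 = 1.34 SD; arm-by-category difference = sqrt(4/5) x 2.12 = 1.90 SD.

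**Allocation.** If the even/odd rule in protocol 4.3 meant independent draws, exactly 5 v 5 in both categories would have probability (252/1024)² = 6%.

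**The case against.** The strongest reply has four parts.

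- *The named primary analysis hardly needs category.* The SAP says mean change, and a stable gap cancels from change. This largely stands. The larger pain figures need either comparison of levels, which the SAP's later phrase about differences in pain scores leaves open, or a gap that grows after the starting score.
- *Stratifying the medication test is not clearly better.* This stands too. A reader might infer that the planned Mann-Whitney test should be replaced because it has 22% power against 30% at a 1 SD gap. That holds only for an equal effect in both categories, which the hypothesis in 1.1 B doubts. If the effect lies only in the opioid-history category, the pooled test is ahead at gaps of 0.5 and 1 SD and behind only at 2 SD. At a gap of 0.5 SD with equal effects the two differ by about 2 points.
- *Category is already covered by the SUD clause.* Perhaps. The clause sits in the sentence about the two arms and may mean by-arm results. If so, one sentence settles it for pain, but medication intake remains uncovered.
- *This is a 20-woman pilot with no power target.* True, and at 5 per cell only description is possible. That argues for exploratory labelling and intervals. It does not argue against reporting the effects that the protocol says it expects.

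**Conclusion.** The point holds as a low-cost improvement in precision and clarity. Neither named method includes category, and the protocol's category-specific hypothesis has no clearly planned estimate. For pain, adding category to a model with a pre-TENS score gains 1-6% in interval width under a stable gap and about 11-22% under a growing one, and costs about 0.5% with no gap. For medication, the pooled test is conservative when intake differs between categories, but which test has more power depends on the size of the gap and on where the TENS effect lies.

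A reader might infer that leaving out category biases the result. With 5 v 5 in each category it does not. Protocol 1.3 and 1.5, and the pairs in 6.3 A, point to enforced balance, though 4.3 does not say how it is reached. Only under independent draws could chance imbalance shift the unadjusted estimate. Nor do the documents support a claim that the trial would be adequately powered once category is included: no version here exceeds 60% power at the illustrative effect.

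Every gap, correlation and effect size is an assumption, and the pain results simplify the repeated measures to two scores.

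**What to change.** 1. **Pain.** In the mixed-effects model that the SAP already mentions, include as covariates the last score before TENS starts at 8 hours (the same time point in controls) and opioid-history category. Daily medians do not serve as the starting score, since they can mix scores from before and after the device is switched on.
2. **By category.** Report the TENS effect in each category and the arm-by-category difference, with 95% CIs, for pain and for medication intake. Label them exploratory, and state whether this is what the SUD clause means. Expect half-widths of about 1.3 and 1.9 SD without a starting score.
3. **Medication.** Keep the planned Mann-Whitney test. If 5 v 5 was enforced, add a category-stratified exact rank test as a sensitivity analysis. If balance was not enforced, leave it out: with no gap, stratifying then costs about 5 points of power (30% v 25% at 0.74 SD).

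The cost is SAP wording, a little programming and one or two between-patient degrees of freedom. A pre-8-hour score must also be extracted. Protocol 4.11 takes pain ratings from the flowsheets but does not list their times, so availability should be checked. The SAP describes some tests in the past tense; if analysis has begun, these changes must be labelled post hoc.

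Three neighbouring items need separate clarification: which two repeated measures the RMCORR analysis relates, whether maintenance methadone or Subutex counts as intake, and how the even/odd rule in 4.3 yields 5 v 5.

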### **1.5 Sample Size Justification**

This is a pilot feasibility study to evaluate effectiveness and acceptability in our patient population of TENS use throughout delivery hospitalization. We aim to have 20 participants total: 5 in control and 5 in intervention without history of opioid addiction, and 5 in control and 5 in intervention with history of opioid addiction/misuse. This sample size is comparable to other shorter term pilot studies. This pilot study will serve as the basis for larger trials in the future, with larger sample size powered to demonstrate reduction in pain scores. We anticipate recruitment for this trial will take approximately 6-9 months.

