##### **C. Require Number of Subjects to Complete Research**

40

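### The SAP describes the primary pain analysis both as a fixed-effects repeated measures ANOVA and as a mixed-effects procedure; one stated model should replace both descriptions.

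*SAP*

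**What the plan says.** The SAP, under Primary Outcome, compares TENS with usual care on average change in VAS pain "over the course of the inpatient hospital stay". The method is given in one sentence: "Fixed effects repeated measures analysis of variance was used to evaluate the differences in pain scores between groups". Under Missing data it adds: "Mixed-effects procedure was utilized to avoid loss of data from missing values at different time points". That sentence does not name the outcome it covers or any random effect.

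The SAP lists no model terms, covariance structure, scheduled time points, tested contrast, degrees-of-freedom method or significance level.

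Protocol section 6.1 plans something else: "Primary outcome measures of daily median pain scores will be compared using nonparametric statistical methods". On size, Protocol section 1.5 states: "We aim to have 20 participants total: 5 in control and 5 in intervention without history of opioid addiction", with the same split for women with an opioid history. Section 4.5 gives a total of 20, but 40 under "Require Number of Subjects to Complete Research".

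**The concern.** Arm does not vary within a woman. Her repeated scores therefore carry less information about arm than the same number of scores from different women, and the arm comparison needs an error term built from differences between women.

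The two SAP sentences can be read in three ways, with different consequences:

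- **Literal fixed effects.** There is no between-woman error term. If woman is left out, her scores count as independent. If woman is entered as a fixed effect, arm is aliased with woman (20 women plus arm give 21 columns of rank 20), and dividing by the within-woman residual uses too small an error.
- **Classical repeated measures ANOVA.** The arm test is valid, but a woman with any missing score is normally dropped. That conflicts with the Missing data sentence.
- **Mixed model with arm and time as its fixed effects.** The analysis is sound and only the label is wrong.

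The interval and p-value for the main pain comparison depend on which reading applies. Both SAP sentences are in the past tense, so a result may already exist. Protocol section 1.5 makes this pilot the basis for larger trials.

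**Working it through.** **Inputs.** From the documents: 5 + 5 + 5 + 5 = 20 women, so 10 per arm (Protocol 1.5). Assumed, because the documents give no figure: K = 3 to 9 scores per woman, equal within-woman correlation ρ = 0.1 to 0.7, and a two-sided 5% test. The plan has no error rate or power figure to reproduce. The entry of 40 subjects in Protocol 4.5 matters little here, because the variance ratios below do not involve the number of women.

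**Mean squares when TENS has no effect.** With score variance σ², the expected mean square is σ²[1 + (K−1)ρ] both for arm and for women within arm. For the within-woman residual it is σ²(1−ρ).

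**Between-woman error.** The ratio is 1, tested on F(1, 18), and the false-positive rate is 5%. Simulation gave 4.5-5.4% in every setting.

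**Woman left out.** The pooled residual is close to σ², so the test statistic is inflated by D = 1 + (K−1)ρ. The rate is about 2[1 − Φ(1.96/√D)]. For K = 6 and ρ = 0.5, D = 3.5 and 1.96/√3.5 = 1.048, which gives 29%.

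**Arm over the within-woman residual.** The inflation is λ = [1 + (K−1)ρ]/(1−ρ), and the rate is P(F(1, 18(K−1)) > F₀.₉₅/λ). For K = 6 and ρ = 0.5, λ = 3.5/0.5 = 7 and 3.947/7 = 0.564 on (1, 90) degrees of freedom, which gives 45%.

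False-positive rate for the arm main effect, woman left out / within-woman residual:

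| Scores per woman | ρ = 0.1 | ρ = 0.3 | ρ = 0.5 | ρ = 0.7 |
|---|---|---|---|---|
| 3 | 7% / 9% | 12% / 19% | 17% / 32% | 21% / 48% |
| 6 | 11% / 13% | 22% / 30% | 29% / 45% | 36% / 61% |
| 9 | 14% / 16% | 29% / 37% | 38% / 53% | 45% / 67% |

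Simulation of 20,000 null trials per setting agrees to within about one percentage point. Results with 5 women per arm are almost the same.

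**Arm-by-time instead of arm.** Tested against the within-woman residual, the simulated rate is about 5% under equal correlation and 6-13% when correlation decays over time (AR(1), 0.5 to 0.9). With woman left out it is 5% or less.

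**Dropping incomplete women.** If 10% of scores were missing independently at each of 6 times (assumed), 0.9⁶ = 0.531 of women would be complete, or 20 × 0.531 = 10.6 of 20.

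**Mixed model at this size.** A normal reference in place of t on 18 df gives P(|t₁₈| > 1.96), about 6.6%. In 600 simulated trials with 4 times, ρ = 0.5 and 15% of scores missing, the rates were 6.3% (normal) and 4.7% (t on 18 df), with a Monte Carlo error of about 1 point.

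**Opioid-history category left out.** Take K = 6, ρ = 0.5 and an assumed category difference of 1 SD of a single score.

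- The variance of a woman's mean is 3.5/6 = 0.583.
- The category adds 20 × 0.5² = 5 to the error sum of squares, so the error mean square becomes 0.583 + 5/18 = 0.861, which is 1.48 times larger.
- The critical value of 2.10 then acts like 2.10 × √1.48 = 2.55, and the rate falls to about 2%. The test loses power.

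**The case against.** A reader might infer that the SAP's ANOVA uses the wrong error term and would find a TENS effect in, say, 20-60% of null trials. The documents do not support that. The SAP never says that woman is omitted, entered as a fixed effect, or that arm is divided by the within-woman residual. It says repeated measures, and the standard form of that analysis tests a between-woman factor against between-woman variation. A mixed model in which arm and time are the fixed effects fits both sentences, and on that reading incomplete women are not lost.

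The rates also depend on three unstated inputs, and with 3 scores and woman left out they are mostly below 20%. The inflation and the loss of incomplete women belong to different readings and cannot both be charged to one model. Average change over the stay can also be read as arm-by-time, which does not show the same inflation. Finally, this is a pilot for which "Power analysis is not performed as this is a pilot study".

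All of this stands. It removes any claim that the analysis was wrong. It does not settle which model was used. The wording about pain differences between groups reads naturally as an arm effect, and the protocol offers no fallback because it plans a different analysis.

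**Conclusion.** The SAP gives two unreconciled descriptions of its primary pain model, and the analysis cannot be reproduced from either. This is certain from the text, as is the departure from the protocol's nonparametric comparison of daily medians.

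The statistical harm is conditional. It requires the literal fixed-effects reading and an arm main-effect contrast. Under the assumptions above, false positives would then be about 7-45% (woman left out) or 9-67% (within-woman residual), against 5% with between-woman error. Under the classical reading the arm test holds 5%, and the cost is lost women. Under the mixed-model reading only the label needs correcting, and the degrees-of-freedom method needs stating.

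The text should be corrected and the model confirmed before the pain result is relied on. This is not a demonstrated error in a result.

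**What to change.** Replace both SAP sentences with one model for pain:

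- a linear mixed model using all available scores;
- woman as a random effect;
- arm, time, arm-by-time and the opioid-history category used in allocation as fixed effects;
- the contrast that represents average change over the stay, named explicitly, with its significance level;
- Kenward-Roger degrees of freedom.

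List the scheduled score times. Re-randomising arm labels across women within category is an optional exact check.

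State that this departs from the nonparametric comparison of daily median pain scores in Protocol section 6.1, and give the reason. Confirm which model produced any existing pain result, and re-run if it differs. Reconcile the entries of 20 and 40 subjects in Protocol section 4.5.

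The cost is a few lines in the SAP and at most one re-run of data already collected. The interval may be wider if the earlier run lacked a between-woman error term.
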